## 11.6 Study Hypotheses

From the two aims, there are two hypotheses:

H1: Multi-dose (alternate) MTZ is superior to the single dose (recommended) for the treatment of TV among HIV-negative women.

H2: Altered vaginal flora (measured by Nugent's score) interferes with the MTZ treatment of TV for the single dose but not the multi-dose.

## 11.7 Sample Size

### Considerations

[figure not shown]
This RCT will allow for evaluation of index dosing of MTZ by BV status. This study examines two hypotheses simultaneously:

H1: Women receiving multi-day MTZ will be less likely to test TV positive at TOC compared to women who receive the single dose MTZ.

H2: This effect (H1) will only be observed among women who have BV (Nugent score  $\geq 7$ ).

From our pilot work, we found the rates of repeat infection at TOC to be 16.2% for single dose and 10.7% for multi dose at a power of 0.80, we will need 1206 subjects. If we account for a 5% Inner Class Correlation (ICC) for correlation of the subjects within the 4 sites using the formula  $1=(M-1)*ICC$ . We will need to inflate by 15%. We will also inflate by 20% to accommodate for our anticipated follow-up for a required sample size of 1664. We will have 1332 evaluable unites at TOC, which will provide adequate power taking into consideration the ICC.

Figure 1.  
Randomization Scheme

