## **11.3 Description of the Analyses**

The TV positive rate will be compared between the two arms for superiority. Additional analyses will be conducted to compare the rates stratified by BV status.

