All analyses will be conducted in SAS by Tulane staff under the direction of [name]. Because we will use strict protocols and employ tight supervision of the study sites and the study populations are similar (mostly African American and underserved) we do not anticipate site variations but we will examine for any differences and if found, we will include a site variable in the models. We do not anticipate a three-way interaction, and our simulations (see below) support that belief. We will, however, run a fully parameterized model including all main effects, first order interactions, and second order interaction before running the primary analysis model (1) above. We will consider any p-value less than 0.05 to be significant and any p-value less than 0.10 as near-significant. If there is unexpected significant or near-significant interaction, we will stratify on BV status and assess the impact of index treatment (single vs. multi-dose) and any possible interaction separately for BV positive and BV negative women.

Additional analyses– The ACASI will allow for examination of index adherence to medication, index knowledge of partner treatment, sexual exposure and the nature of the sexual act and sexual partner, condom use. These factors will be assessed by arm to determine if any confounding occurred and if so, these analyses will be adjusted for these factors or stratified by these factors.

**Figure 4:** Algorithm for determining origin of repeat infection at TOC

**Outcome measures** – The study is powered for repeat infections. Since we will have information on sexual exposure and genotyping, we can also refine this outcome measure to examine treatment failure (H1 & H2) and reinfection and will use the algorithm depicted in figure 4.

All analyses will be conducted in SAS by the Tulane staff under the direction of [name]. As the data collection instruments are designed to

minimize missing data we do not anticipate an excessive amount. However, imputation techniques will be utilized to compensate for missing data (e.g. multiple imputation and maximum likelihood). Sensitivity analyses will be conducted to ensure that the method chosen to account for missing data does not bias the study’s results. Additionally, the characteristics of those who complete the study will be compared to those who drop out to determine whether drop out is informative. If not, multiple imputation methods will be used for initial analyses. If,

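### H2 says the treatment effect exists only in women with BV, but no planned analysis, margin or decision rule can support the word *only*

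*Combined protocol and SAP*

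**What the plan says.** H2 is worded as "This effect (H1) will only be observed among women who have BV" in Section 11.7, and in substance the same way in the Protocol Summary, Section 3.1 and Section 11.13. Sections 11.1 and 11.6 word it differently: altered flora interferes with treatment under the single dose and does not under the multi-dose. That is also a claim of no effect, in a different subgroup.

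The analysis has two parts. Section 11.13 fits a logistic model with treatment, BV and their interaction, and names the differential impact of BV as the test of H2. If an interaction that it calls unexpected reaches p<0.05, or the looser p<0.10, treatment is then assessed "separately for BV positive and BV negative women". Section 11.3 adds, without that condition, that "Additional analyses will be conducted to compare the rates stratified by BV status".

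The sample size concerns the overall comparison only. It takes "rates of repeat infection at TOC to be 16.2% for single dose and 10.7% for multi dose at a power of 0.80", concludes "we will need 1206 subjects", and after inflation expects "We will have 1332 evaluable unites at TOC". I found no BV prevalence for the trial population, no stratum size, no power for the interaction or for BV-negative women, and no margin for absence of effect.

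**The concern.** The *only* in H2 joins two statements: the effect differs by BV status, and it is nil without BV. A significant interaction supports the first. The second is a null claim. It needs a margin and enough precision, and a non-significant test in the BV-negative stratum provides neither. On the shares reported for HIV-positive women, that stratum is also the smaller one, and in the sponsor's earlier trial its overall repeat-infection rate was lower (Table 4: 6.7% vs 16.1% at TOC).

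The misreading is realistic. Section 2.2 concludes that BV has no effect on outcome under the 7-day course. The Table 4 row behind that statement has RR 1.07 with a 95% CI of 0.28 to 4.04. Yet Section 2.1.3 faults an early study for inferring equivalence from p=0.06 without the power for it.

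Sections 2.1 and 4.1 say the results will be used to refine treatment recommendations. A claim that BV-negative women gain nothing from the longer regimen would feed directly into that guidance, so the design has to be able to support it.

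**Working it through.** **1. The plan's own figure.** Inputs from Section 11.7: p1 = 0.162, p2 = 0.107, power 0.80. Alpha 0.05 comes from Section 11.13; two-sided is my assumption. With mean rate 0.1345:

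n per arm = [1.960 × √(2 × 0.1345 × 0.8655) + 0.842 × √(0.162 × 0.838 + 0.107 × 0.893)]² / 0.055² = 602.9, so 603 per arm and 1206 in total, as stated.

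1206 × 1.15 × 1.20 = 1664.3, matching 1664. 1664 × 0.80 = 1331, against 1332 stated. All of this sizes H1 across both strata together.

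**2. Size of the BV-negative stratum.** The documents give no share for HIV-negative women with TV. Section 2.2 gives 61.0% BV among HIV-positive women with TV, so 39% BV-negative. Table 4 gives 155/230 = 67.4%, so 32.6% BV-negative. I take BV as measured at baseline; the model description in 11.13 does not say which visit.

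- 1332 × 0.326 = 434 (217 per arm)
- 1332 × 0.39 = 519 (about 260 per arm)

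**3. Precision if the true BV-negative effect is zero.** Half-width = 1.96 × √(2p(1−p)/n):

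| Rate in both arms | n = 260 per arm | n = 217 per arm |
|---|---|---|
| 7% | 4.4 points | 4.8 points |
| 10.7% | 5.3 points | 5.8 points |

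The planned overall difference is 16.2 − 10.7 = 5.5 points. At 10.7%, with 50% BV-negative the half-width is 4.7 points. With 71% BV-negative (from the 29% BV prevalence in the national sample in Section 2.2) it is 3.9.

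With an assumed margin of 5.5 points, two one-sided 5% tests would show absence with power of only 17% (n=434) to 30% (n=519) at a 10.7% rate. At a 6% rate, power is 56% to 68%.

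**4. Power if BV-negative women have the full planned effect (16.2% vs 10.7%).** It is 39% at n=434 and 45% at n=519. For 80% power in that stratum alone, 1206 evaluable BV-negative women are needed: 1206/0.326 ≈ 3,700 or 1206/0.39 ≈ 3,090 evaluable in total, against 1332.

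**5. What the planned steps would show.** I simulated 200,000 trials per scenario with 666 women per arm and pooled z tests in each stratum. The interaction statistic is the difference of the two log odds ratios divided by √Σ[1/x + 1/(n−x)] over the four cells, with 0.5 added to each count.

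- *Equal relative effect* (RR 10.7/16.2 = 0.66 in both strata, so *only* is false). Requiring the interaction as well as a significant BV-positive and a non-significant BV-negative result, the false pattern occurs in about 2-3% of trials at p<0.05 and 4-7% at p<0.10.
- *Larger effect with BV, real effect without.* BV-positive rates are rounded from Table 4 (23.8% vs 8.0%). BV-negative rates are assumed at 8.0% vs 5.3% (8.0 × 0.66 = 5.3). The interaction passes p<0.10 in 60-64% of trials. In 95-98% of those the BV-negative test is non-significant. So 59-61% of all trials display the *only with BV* pattern although BV-negative women benefit.

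The second scenario is favourable to the interaction test. Its overall difference is 0.61 × 15.8 + 0.39 × 2.7 = 10.7 points, or 0.674 × 15.8 + 0.326 × 2.7 = 11.5 points, about twice the planned 5.5. At an average difference of 5.5 points with a truly zero BV-negative effect (10.7% in the other three cells), the interaction reaches p<0.10 in 57-66% of trials and p<0.05 in 44-54%. For a partial BV-negative effect at the planned overall size, I would therefore expect a figure between the first scenario and 57-66%.

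**The case against.** The strongest objection is that the plan does not test H2 by comparing stratum p-values. Section 11.13 assigns H2 to the interaction, and the separate analysis there follows a significant or near-significant interaction. No section says that a non-significant BV-negative result counts as support for H2.

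This defeats a stronger reading that is tempting: that the plan would give a false *only* in half or more of trials. The pattern of significance with BV and not without does occur in about 53-58% of simulated trials with equal relative effects. It does so only if the interaction is ignored, BV doubles the risk and 61-67% of women have BV. At 29-50% BV it is 11-43%, and with the planned interaction required it is about 2-7%. The documents do not support the larger figure as a property of the plan.

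A second objection is that the stratum is not hopeless. If BV-negative rates are near 7%, a zero estimate with a half-width of 4.4-4.8 points would exclude 5.5. That is correct, but no margin is set, the rate is unknown, and at 10.7% the interval is about as wide as the design effect.

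A third is that rewording H2 as a larger reduction is ambiguous unless the scale is named. With equal relative effects and doubled risk, the absolute reduction is twice as large with BV (2p − 2 × 0.66p), although there is no difference on the relative scale. This stands, and the fix names the scale.

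What remains is that a significant interaction shows that two effects differ. It cannot show that one of them is zero.

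**Conclusion.** The concern holds as a gap between the hypothesis and the planned analyses. H2 as written contains a null claim that neither the interaction test nor the stratified comparison can establish, and no margin, stratum power or decision rule fills the gap. This conclusion does not depend on the simulations.

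The size does depend on assumptions. The BV share is borrowed from HIV-positive women. The BV-negative rates of 8.0% vs 5.3% are assumed; the few BV-negative women in Table 4 had 2/35 vs 3/40. The p<0.10 step is read as applying to the treatment-by-BV term, although the sentence in 11.13 follows a remark about a three-way interaction. On that footing the false *only* pattern ranges from about 2-7% (equal relative effects) to about 59-61% (larger effect with BV, real effect without). The sample size for H1 is reproduced and is not challenged by this point.

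**What to change.** In Sections 3.1, 11.7 and 11.13, and in the Protocol Summary for consistency, restate H2 as effect modification: the reduction in the odds of repeat infection with multi-dose versus single-dose MTZ is greater in women with BV than in women without. Name the treatment-by-BV interaction in the logistic model, on the odds-ratio scale, as its test. Align the wording in 11.6 and 11.1, which also claims no effect, in that case under the multi-dose.

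Report odds ratios and risk differences with 95% CIs in both strata, whatever the interaction shows. State in 11.13 that a non-significant BV-negative result will not be reported as absence of effect.

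The cost is rewording and one reporting rule, with no added participants, visits or tests. The downside is a less emphatic claim. If the sponsor wishes to keep *only*, it would need a pre-specified margin and power for BV-negative women, which the planned 1332 evaluable women may well not provide.

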If a participant's clinical TV positive test result is not confirmed TV-positive by InPouch culture or NAAT, she will be withdrawn from the study. These testing procedures and de-enrollment potential will be fully explained in the consent form. Women will receive \$20 compensation after completion of the baseline enrollment visit. Women will receive a study contact card that has all contact information for study personnel so that she may contact staff in case of appointment change, questions, or adverse events. She will be instructed to keep this card during the course of the study period. If she is withdrawn, she will keep her baseline compensation but told she will not need to attend her follow-up visits.

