## **11.4 Measures to Minimize Bias**

### **Enrollment/ Randomization/ Masking Procedures**

After eligibility is assessed, informed consent is obtained and the woman has completed the ACASI survey and self-swab collection, she will be randomized to treatment arm. A blocked randomization scheme will be used to avoid “runs” in the randomization process. Each site will have its own blocked randomization scheme. Pre-numbered, sealed envelopes will be selected sequentially and opened for each participant who will then be enrolled in the indicated treatment arm. Because we are conducting a phase III trial and behaviors associated with the interventions are important, we will not attempt to make the single dose mimic a 7-day dose by supplementing with placebo. The trial will, therefore, be un-blinded. There will be no replacement of participants who discontinue early. Enrollment will continue through two months prior to study end.

Study personnel will know which arm the participant was randomized to. This information will not be disclosed to laboratory personnel. The Program Manager will periodically ensure that all participants were randomized to the correct treatment arm as indicated in the randomization scheme. Any discrepancies will be immediately discussed with investigators to prevent further error.

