## 11.8 Maintenance of Trial Treatment Randomization Codes

Randomization will occur at the end of each baseline study visit. Randomization codes will be determined by a block randomization strategy at each site. Sealed envelopes will contain a study identification number on the outside and the randomization arm on the inside. Study staff will chose randomization envelopes sequentially and only open the card after enrollment, survey and specimen collection has occurred. There will be a separate staff member who will create and number the envelopes thereby shielding clinic study staff from knowing the randomization scheme. No study staff at the clinic will have access to the randomization database or numbering scheme. Every six months, a randomization interim analysis will be performed by Tulane staff for DSMB review to ensure that the randomization strategy is successful. The randomization arm will be noted on the study file and in the participant's data once the baseline visit is completed. No laboratory or clinical staff will have access to the randomization database.

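### Section 11.7 inflates for site correlation with the number of sites as cluster size and under-allows for loss, so its 1332 evaluable women fall below its own 1387; H1 power at the assumed rates is not harmed

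*Combined protocol and SAP*

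**What the plan says.** Section 11.7 takes repeat-infection rates at test of cure of 16.2% (single dose) and 10.7% (multi-dose) and states that "at a power of 0.80, we will need 1206 subjects". It then adjusts for site: "If we account for a 5% Inner Class Correlation (ICC) for correlation of the subjects within the 4 sites using the formula", followed by a formula in (M - 1) and ICC and an inflation of 15%. M is not defined. Next comes loss: "We will also inflate by 20% to accommodate for our anticipated follow-up for a required sample size of 1664". The paragraph concludes: "We will have 1332 evaluable unites at TOC, which will provide adequate power taking into consideration the ICC".

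Three other parts of the document bear on this.

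- **Randomization.** Women are allocated individually within site. Section 11.4 says "Each site will have its own blocked randomization scheme" and section 11.8 says "Randomization codes will be determined by a block randomization strategy at each site".
- **Site in the analysis.** Section 11.13 leaves this open: "we will examine for any differences and if found, we will include a site variable in the models".
- **Number of sites.** Sections 5.1, 11.9 and 12 give three; sections 11.2, 11.7 and 14.4 give four.

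**The concern.** Each step after 1206 has a problem.

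1. A cluster design effect, 1 + (M - 1) x ICC, takes M as the number of participants per cluster. A 15% inflation at ICC 0.05 arises only with M = 4, the stated number of sites.
2. The design effect answers a question this trial does not pose. It applies when whole sites are allocated to arms. Here both arms are present in every site in blocked proportion, so differences between sites largely cancel from the arm comparison.
3. If 20% are lost, the evaluable target must be divided by 0.8. Multiplying by 1.2 leaves too few, so the closing adequacy statement contradicts the steps before it.

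At stake is the stated justification for the size of a phase III trial, and a reader's ability to tell how much loss the trial can bear. That second point matters because some enrolled women drop out of the evaluable set for a reason other than missed follow-up. Under section 8.2, a woman whose clinical result "is not confirmed TV-positive by InPouch culture or NAAT, she will be withdrawn from the study"; section 9.10 has a similar criterion for a positive wet prep. The readable text of 11.7 allows for follow-up only.

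**Working it through.** **Inputs.** Section 11.7: 16.2% v 10.7%, power 0.80, ICC 0.05, 4 sites, 20% loss, totals 1206, 1664 and 1332. Section 6.1.1.1: 1:1 allocation, 832 per arm. Section 11.13: significance at 0.05. Sidedness is not stated; two-sided is assumed because it reproduces 1206.

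**Reproducing 1206.** Pooled two-proportion formula, mean rate 0.1345, no continuity correction:

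n per arm = [1.960 x sqrt(2 x 0.1345 x 0.8655) + 0.8416 x sqrt(0.162 x 0.838 + 0.107 x 0.893)]^2 / 0.055^2 = 602.9, so 603 per arm and 1206 in total. A one-sided test would give 950.

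**Reproducing 1664 and 1332.**

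- 1 + (4 - 1) x 0.05 = 1.15
- 1206 x 1.15 = 1386.9, the plan's own evaluable target (1387)
- 1386.9 x 1.2 = 1664.3, stated as 1664
- 1664 x 0.8 = 1331.2, stated as 1332

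The chain matches the printed figures to rounding, so there is little doubt how 1664 was built. The formula is printed with an equals sign where a plus is presumably meant; that is not counted as an error.

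**The loss step.** The plan's target needs 1386.9 / 0.8 = 1734 enrolled, which is 70 more than 1664. With 20% loss from 1664, the 1332 evaluable are 1387 - 1332 = 55 short (4.0%). The loss that 1664 can bear on these terms is 1 - 1386.9/1664 = 16.7%. The effective size is 1332/1.15 = 1158.

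**The ICC step.** With M as women per site, 1332/4 = 333 gives 1 + 332 x 0.05 = 17.6, and 1332/3 = 444 gives 1 + 443 x 0.05 = 23.15. Neither can have been intended. Under the plan's own rule three sites would give 10%, and 1206 x 1.10 x 1.2 = 1592. The disagreement on site count therefore feeds directly into the sample size.

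**Why no design effect applies.** With 1:1 allocation within each site, the variance of the arm difference contains only within-site variation, about (1 - ICC) = 0.95 of the simple binomial variance, not 1.15 of it.

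This was checked by simulation: 200,000 trials, N = 1332, equal sites, a common odds ratio, arm means 16.2% and 10.7%, ICC 0.05. The assumed single-dose rates by site were 6.1/16.2/26.3% for three sites or 8.0/8.0/24.4/24.4% for four. The variance ratio was 0.95 in both.

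| Test | Type I error | Power |
|---|---|---|
| Unadjusted | 4.5% | 84.6% |
| Mantel-Haenszel by site | 5.0% | 85.5% |

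**Power for 16.2% v 10.7% (two-sided 0.05).**

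| Evaluable N | Power |
|---|---|
| 1158 (1332 charged with the 1.15 factor) | 78.4% |
| 1206 | 80.0% |
| 1332 (no design effect) | 83.8% |
| 1387 (no design effect) | 85.2% |

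Without the design effect, 80% power is kept until 1 - 1206/1664 = 27.5% of enrolled women are not evaluable.

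**The case against.** The strongest reply is that nothing practical follows. The two faults offset: an unneeded 15% more than covers the missed loss allowance, H1 keeps 83.8% power, and even on the plan's ICC terms the shortfall is 1.6 points. This is right about consequence, and it is why no one need be added. It does not rescue the text, whose adequacy statement is false by its own numbers.

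A second reply is that the margin is less firm than it looks. If site rates are drawn at random with ICC 0.05, average power is 0.80 to 0.81 at 1332 and 0.76 to 0.77 at 1206. The input rates also match no table in the protocol: Table 2 has 16.8% v 8.5% and Table 4 has 18.3% v 7.8%, both in HIV-positive women. The single-dose rate in the sponsor's own HIV-negative study was 8.0% (24/301). At that rate and 1332 evaluable, power would be about 51% with the same relative risk or about 57% with the same odds ratio, both assumptions. These figures stand, but they describe uncertainty about the rates, which no design effect corrects. What follows is that any restated power must name the rates it depends on. The simulations also assume one odds ratio for all sites; variation in effect by site was not examined.

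Third, a figure in 11.7 and the simulations mentioned in 11.13 are not in the text reviewed and may address H2. No claim is made that H2 power is missing. The 1206 at 0.80 reproduces exactly from the two overall arm rates, so that figure belongs to H1.

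Finally, adding site to the model is partly a preference. It is worth about one point of power. The better reason is that it removes a data-driven choice.

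**Conclusion.** The concern holds. As written, section 11.7 uses the number of sites as the cluster size, applies a cluster design effect to individually randomized women, and under-allows for loss. Its 1332 evaluable are 55 below its own 1387: 78.4% power instead of 80%, and 16.7% tolerable loss instead of 20%.

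For H1, 1664 remains sufficient at the plan's rates. It gives 83.8% power at 1332 and a margin to 27.5% not evaluable, which 11.7 does not state. This rests on 16.2% v 10.7%, a two-sided 0.05 test, individual randomization within site and a common odds ratio across sites. The defect is in the justification and should be corrected; it does not threaten the H1 comparison at those rates.

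**What to change.** Rewrite 11.7 and adjust 11.13; enrolment stays at 1664.

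1. Delete the ICC inflation and the reference to the ICC in the adequacy statement. State instead that 1206 evaluable women give 80% power for 16.2% v 10.7% in an unadjusted two-sided 0.05 comparison. Add that 1664 enrolled with 20% not evaluable leaves about 1331 and about 84% power. Add also that 80% is kept if up to about 27% are not evaluable for any reason, including withdrawal because infection was not confirmed. Make all of this explicitly conditional on those rates.
2. In 11.13, pre-specify that the primary model includes or stratifies by site, replacing the plan to add site only if differences are found.
3. Reconcile four sites (11.2, 11.7, 14.4) with three (5.1, 11.9, 12).
4. State that the 0.80 power refers to H1.

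The cost is protocol and SAP wording only. No women, visits or data are added, and randomization is already blocked by site.
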